**Table JFCU.9.1. Treatment Regimens/Dosing Schedule**

#### Part A

Cohort	Drug	Dose	Day	Infusion duration
Cohort 1	Necitumumab	800 mg absolute dose I.V. infusion	Days 1 and 8	over 60 minutes a (±5 minutes)
	Abemaciclib	100 mg Q12H	Days 1 - 21	
Cohort 2	Necitumumab	800 mg absolute dose I.V. infusion	Days 1 and 8	over 60 minutes a (±5 minutes)
	Abemaciclib	150 mg Q12H	Days 1 - 21	
Cohort 3	Necitumumab	800 mg absolute dose I.V. infusion	Days 1 and 8	over 60 minutes a (±5 minutes)
	Abemaciclib	200 mg Q12H	Days 1 - 21	

#### Part B

Drug	Dose	Day	Infusion duration
Necitumumab	800 mg absolute dose I.V. infusion	Days 1 and 8	over 60 minutes a (±5 minutes)
Abemaciclib	Dose from Part A Q12H	Days 1 - 21	

Abbreviations: IV= intravenously; Q12H = every 12 hours.

a At the time of approval of the JFCU(b) protocol amendment, all patients who are still on the study will be administered necitumumab I.V. infusion over 60 minutes (±5 minutes).

The individual recommended dose for necitumumab is 800 mg on Day 1 and Day 8 every 21 days and 200 mg Q12H for abemaciclib. For this reason, further dose escalation beyond Cohort 3 will not be tested.

Hypersensitivity/infusion-related reactions may occur during or following administration of necitumumab (see Section 9.3.2.2.3.1.1 for a definition of Grade 3 and 4 hypersensitivity/infusion-related reactions). As a routine precaution, patients treated with necitumumab should be observed closely for any potential adverse effects by the medical staff from the start of the infusion until at least 1 hour after the end of the infusion in an area with resuscitation equipment and other agents (for example, epinephrine or prednisolone equivalents) available.

The investigator or his/her designee is responsible for the following:

- explaining the correct use of the drugs and planned duration of each individual's treatment to the patient,
- verifying that instructions are followed properly,
- maintaining accurate records of study drug dispensing and collection,
- and returning all unused medication to Lilly or its designee at the end of the study.

**Note:** In some cases, sites may destroy the material if, during the investigator site selection, the evaluator has verified and documented that the site has appropriate facilities and written procedures to dispose clinical trial materials.

Patients will be instructed to contact the investigator as soon as possible if they have a complaint or problem with the study drug so that the situation can be assessed.

## 9.2. Materials and Supplies

All study treatment materials will be provided by Lilly. Clinical trial materials will be labeled according to the country's regulatory requirements.

Necitumumab is a sterile and preservative-free solution for I.V. infusion supplied in the following formulation:

- Necitumumab at a final concentration of 16 mg/mL (800 mg/50 mL) contained in single-use vials, in a formulation of 10 mM citrate, 40 mM sodium chloride, 133 mM glycine, 50 mM mannitol, 0.01% polysorbate-80, pH 6.0.

All excipients used in the formulation of necitumumab are of pharmacopeial grade. No animal-derived components are used in the manufacture of necitumumab excipients. Refer to the IB for detailed information.

Abemaciclib will be supplied by Lilly as capsules for oral administration. Abemaciclib capsules should be stored according to the temperature range listed on the product label, and should not be opened, crushed, or chewed.

### 9.3. Method of Assignment to Treatment

An interactive web response system will be used for treatment assignment in both Parts A and B of the study.

#### 9.3.1. Selection and Timing of Doses

The first treatment will be administered within 7 days of enrollment. Study treatment will be administered as described in Section 9.1.

A cycle is defined as an interval of 21 days.

Administration of necitumumab Day 1 dose will trigger the start of a new cycle. Infusions administered within 3 days before or after the planned infusion time point due to holidays, weekends, bad weather, or other unforeseen circumstances will be permitted and not counted as a protocol deviation. The necitumumab Day 8 dose can be delayed up to 5 days. Beyond that, the Day 8 dose will have to be omitted in order to maintain the 21 day cycle. **A minimum of 7 days' interval between any necitumumab dose must be maintained.**

Abemaciclib will be taken orally every 12 ( $\pm 2$ ) hours on Days 1 through 21 of a 21-day cycle, for a total of 42 doses per cycle. During all cycles, abemaciclib should be taken at approximately the same times each day. If a patient misses or vomits abemaciclib, that dose should be omitted.

In the event of a cycle delay due to logistical reasons (for example, due to patient availability), the patient should continue on abemaciclib treatment. If abemaciclib is interrupted as a result of not having sufficient drug supply, the treatment may be delayed up to 5 days (and not be considered a protocol violation). In exceptional circumstances, a delay  $>5$  days is permitted upon agreement between the investigator and the Lilly CRP.

A patient may continue to receive study treatment until he or she meets 1 or more of the specified reasons for discontinuation (as described in Section 7.3).

#### 9.3.2. Special Treatment Considerations

##### 9.3.2.1. Dose-Limiting Toxicity (Part A)

A dose-limiting toxicity (DLT) is defined as one of the following AEs, occurring in Cycle 1 if considered to be definitely, probably, or possibly related to necitumumab and abemaciclib. The following list will define DLT:

- Grade 3 or 4 nonhematologic toxicity according to the NCI CTCAE Version 4.0 except for nausea, vomiting, diarrhea, or electrolyte disturbance (see below)
- Grade 3 or 4 nausea, vomiting, or diarrhea that persists more than 2 days despite maximal supportive intervention
- Grade 3 thrombocytopenia with bleeding requiring transfusion
- Grade 4 thrombocytopenia with or without bleeding

- Grade 4 neutropenia that persists more than 5 days
- Grade 3 or 4 neutropenia with fever
- Grade  $\geq 3$  skin toxicity despite best supportive care
- If a total at least 75% of the planned dose for both agents cannot be administered in the first cycle due to toxicity

DLT is defined by sponsor and Principal Investigator.

The following toxicities will not be considered DLTs if they are transient (<7 days) with full supportive therapy:

- Grade 3 arthralgia or myalgia
- Grade 3 asthenia or fatigue
- Grade 3 constipation

The following toxicities will not be considered DLTs:

- Grade 3 injection-site reaction
- Grade 3 elevation of transaminases lasting <7 days
- Grade 3 elevation of serum-bilirubin lasting <7 days
- Transient Grade 3 elevation or decrease of electrolytes
- Grade 3 or 4 hypersensitivity

If a Grade 3 or 4 infusion-related reaction (hypersensitivity) to necitumumab occurs, this event will not be considered a DLT; the patient will not receive any further study therapy and will be replaced in the study by a new patient.

### **9.3.2.2. Dose Adjustments and Delays**

#### **9.3.2.2.1. Abemaciclib**

Abemaciclib dose adjustments are allowed both within a cycle and between cycles. Abemaciclib must be reduced sequentially by 1 dose level.

An abemaciclib dose level below 100 mg Q12H is not allowed. For patients starting at abemaciclib 100 mg Q12H, no further dose reduction is permitted. For patients starting at dose level 150 mg Q12H, only 1 dose reduction is allowed.

Abemaciclib may be held up to 14 days to permit sufficient time for recovery from the toxicity. If a dose suspension occurs, the investigator may resume abemaciclib dosing at the same dose level for the remainder of the study or at reduced dose (assuming resolution to at least Grade 1 for nonhematologic and at least Grade 2 for hematologic toxicity). If the patient experiences the same toxicity with the same or greater severity (CTCAE grade) requiring a dose suspension within a cycle or at start of the next cycle, the patient must be dose reduced and not re-challenged a second time at the prior dose level.

If a patient experiences CTCAE Grade 4 hematologic toxicity possibly related to abemaciclib, then dosing must be suspended (until the toxicity resolves to either baseline or at least Grade 2) and the dose of abemaciclib must be reduced as outlined in [Table JFCU.9.2](#).

If a patient experiences CTCAE Grade  $\geq 3$  nonhematologic toxicity possibly related to abemaciclib, then dosing must be suspended (until the toxicity resolves to either baseline or at least Grade 1) and the dose of abemaciclib must be reduced as outlined in [Table JFCU.9.2](#).

If a patient experiences persistent or recurrent Grade 2 nonhematologic toxicity (except diarrhea) possibly related to abemaciclib that does not resolve with maximal supportive measures within 3 days (as outlined in [Section 9.5.3](#)) to either baseline or Grade 1, then dosing should be suspended (until the toxicity resolves to either baseline or at least Grade 1), and the dose of abemaciclib may be reduced as outlined in [Table JFCU.9.2](#).

For patients requiring dose reduction(s), any re-escalation to a prior dose level is permitted only after consultation with the Lilly CRP. After re-escalation, subsequent dose adjustments should be based on the dose of abemaciclib that the patient is currently receiving.

**Table JFCU.9.2. Dose Adjustments of Abemaciclib**

Dose Adjustment Level	Oral Dose	Frequency
0	200 mg	Every 12 hours
1	150 mg	Every 12 hours
2	100 mg	Every 12 hours

Abemaciclib must be discontinued if further dose reduction is required beyond 100 mg every 12 hours. The patient may continue to receive necitumumab as a single agent.

Patients not recovering from toxicity within 14 days should be considered for discontinuation from abemaciclib treatment.

#### **9.3.2.2.1.1. Guidance for Monitoring of Renal Function in Patients on Abemaciclib**

Abemaciclib has been shown to increase serum creatinine due to inhibition of renal tubular secretion of creatinine without affecting cystatin C calculated glomerular filtration rate. Increases in serum creatinine occurred within the first 2 weeks of treatment, remained stable through the treatment period, and were reversible upon treatment discontinuation. If deterioration of renal function is suspected, serum creatinine should not be the only measure used to assess a patient's renal function. Dose alterations (omission, reduction, or discontinuation) should not solely be based on interpretation of serum creatinine values because these may not reflect renal function.

#### **9.3.2.2.2. Necitumumab**

Prior to each administration of necitumumab all toxicities associated with necitumumab must have resolved to Grade  $\leq 2$  (except for alopecia and skin toxicity) or baseline. Pretreatment laboratory data may not be older than 72 hours (Day 1 of each cycle) or 24 hours (Day 8 of each cycle).

If the criteria are not met at the time of a planned treatment, the following general rules for the management of treatment delays apply:

- In the case of necitumumab-related toxicity, administration of necitumumab will be at the reduced dose (refer to Section 9.3.2.2.3) or interrupted, but abemaciclib will continue according to the planned schedule.
- If administration of necitumumab is delayed for more than 6 weeks (2 cycles) after Day 1 of the most recent treatment cycle the patient should be discontinued from necitumumab treatment.

### **9.3.2.2.3. Necitumumab Dose Modifications**

The following are general dose-modification guidelines for toxicity associated with necitumumab. Please see Section 9.3.2.2.3.1 for specific information on the management of necitumumab-related hypersensitivity/infusion-related reactions, skin reactions, conjunctivitis, and hypomagnesemia.

Dose modifications are permitted for necitumumab following non-life threatening reversible CTCAE Grade  $\geq 3$  AEs that require delay of necitumumab treatment for up to 6 weeks following Day 1 of the most recent treatment cycle. In this setting, necitumumab may be readministered at a reduced dose (600 mg) if necessary only if AE is resolved to Grade  $\leq 2$ . A second dose reduction (to 400 mg) is permitted for this level of event (Grade  $\geq 3$ ).

If a patient experiences CTCAE Grade  $\geq 3$  hematologic toxicity possibly related to necitumumab, then dosing must be suspended (until the toxicity resolves to either baseline or at least Grade 2) and the dose of necitumumab must be reduced by 1 dose level (see below).

If a patient experiences  $\geq$  CTCAE Grade 3 nonhematologic toxicity possibly related to necitumumab, then dosing must be suspended (until the toxicity resolves to either baseline or at least Grade 1) and the dose of necitumumab must be reduced by 1 dose level (see below).

Events that necessitate more than 2 dose reductions warrant discontinuation from necitumumab treatment. Following a dose reduction, the dose of necitumumab may be re-escalated to the pre-reduction dose, provided that at least 2 administrations have elapsed following the first administration of the reduced dose, and only after consultation with the Lilly CRP. For dose modifications in response to specific AEs related to necitumumab, please see Section 9.3.2.2.3.1.

Patients who enter the study with symptoms or laboratory values equivalent to NCI-CTCAE Version 4.0 Grade 1-2 AEs should not have dose reductions related to the persistence or mild worsening (for example, from Grade 1 to Grade 2) of those symptoms or laboratory values. Dose reductions (to 400 mg) are warranted in the setting of Grade 1-2 baseline symptoms or laboratory values that worsen to Grade  $\geq 3$  during treatment.

In the event of alterations of necitumumab therapy due to a necitumumab-related toxicity, abemaciclib need not be altered, and the planned abemaciclib schedule should be maintained. Similarly, necitumumab therapy should not be delayed for abemaciclib-related toxicities.

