2	
 
Stop the infusion, and resume the infusion when the infusion reaction has resolved to ≤ Grade 1; decrease infusion rate by 50% when the infusion resumes.a
 
Monitor patient for worsening of condition.
 
If necessary, administer diphenhydramine hydrochloride 50 mg I.V. (or equivalent), acetaminophen 650 mg orally for fever, and oxygen.
 
For all subsequent infusions, premedicate with diphenhydramine hydrochloride 50 mg I.V. (or equivalent); additional premedication may be administered at the investigator's discretion.
 
	
 
Stop the infusion, and resume the infusion when the infusion reaction has resolved to ≤ Grade 1; decrease infusion rate by 50% when the infusion resumes.a
 
Administer dexamethasone 10 mg I.V. (or equivalent).
 
Monitor patient for worsening of condition.
 
If necessary, administer diphenhydramine hydrochloride 50 mg I.V. (or equivalent), acetaminophen 650 mg orally for fever, and oxygen.
 
For all subsequent infusions, premedicate with diphenhydramine hydrochloride 50 mg I.V. (or equivalent), acetaminophen 650 mg orally (or equivalent), and dexamethasone 10 mg I.V. (or equivalent); additional premedication may be administered at the investigator's discretion.
 

3-4	
 
Stop the infusion and disconnect the infusion tubing from the patient.
 
Administer diphenhydramine hydrochloride 50 mg I.V. (or equivalent), dexamethasone 10 mg I.V. (or equivalent), bronchodilators for bronchospasm, epinephrine, and other medications / treatments as medically indicated.
 
Hospital admission may be indicated.
 
Permanently discontinue necitumumab.
 
	N/A

Abbreviations: I.V. = intravenously; N/A = not applicable; NCI-CTCAE = National Cancer Institute-Common Terminology Criteria for Adverse Events.

a Once the infusion rate has been reduced for a Grade 1 or 2 hypersensitivity/infusion-related reaction, it is recommended that the lower infusion rate be utilized for all subsequent infusions. The infusion duration should not exceed 2 hours.

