#### **9.3.2.2.3.1.6. Thromboembolic Events**

In the Phase 3 study JFCC, there was an increase in venous thromboembolic events (VTEs) and arterial thromboembolic events (ATEs) in the investigational arm (necitumumab in combination with gemcitabine and cisplatin) compared to the active control arm (gemcitabine and cisplatin). The relative risk of VTEs or ATEs was approximately 3-fold higher in patients with a reported history of VTEs or ATEs.

In the Phase 3 study JFCB, an increased rate of serious thromboembolic events, including fatal events, has been observed for the combination of necitumumab with pemetrexed and cisplatin as compared with treatment with pemetrexed and cisplatin alone in patients with nonsquamous NSCLC. Administration of necitumumab in combination with pemetrexed and cisplatin is not recommended.

No safety signal with regard to thromboembolic events, including fatal events, has been identified for necitumumab in completed clinical trials when administered as monotherapy or in combination with mFOLFOX-6 chemotherapy.

Treatment of any thromboembolic events occurring under necitumumab treatment should be as clinically indicated according to local standards, and the continuation of necitumumab therapy in these cases should be decided by the investigator after thorough risk-benefit assessment for the individual patient.

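### Protocol 9.3.2.2.3 gives inconsistent necitumumab dosing rules for related life-threatening toxicity that has no event-specific rule, and does not say how they rank against the thromboembolic section

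*Protocol*

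**What the plan says.** Protocol 9.3.2.2.3 presents itself as general guidance. Its opening paragraph sends the reader to 9.3.2.2.3.1 for four named topics: infusion-related reactions, skin reactions, conjunctivitis and hypomagnesemia. The rules then follow.

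- **Paragraph 2 (permission).** "Dose modifications are permitted for necitumumab following non-life threatening reversible CTCAE Grade" 3 or higher events that delay treatment by up to 6 weeks. It continues: "In this setting, necitumumab may be readministered at a reduced dose (600 mg) if necessary only if AE is resolved to Grade" 2 or lower. A second reduction, to 400 mg, is also allowed.
- **Paragraph 3 (hematologic, Grade 3 or higher).** "hematologic toxicity possibly related to necitumumab, then dosing must be suspended (until the toxicity resolves to either baseline or at least Grade 2"). A one-level reduction is then mandatory.
- **Paragraph 4 (nonhematologic, Grade 3 or higher).** At or above "CTCAE Grade 3 nonhematologic toxicity possibly related to necitumumab, then dosing must be suspended", here until baseline or at least Grade 1, again with a mandatory one-level reduction.
- **Paragraph 5 (deferral).** "For dose modifications in response to specific AEs related to necitumumab, please see Section 9.3.2.2.3.1".

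In the event-specific sections, a Grade 3-4 infusion reaction has the instruction "Permanently discontinue necitumumab" (Table JFCU.9.3), and a Grade 4 skin reaction likewise ends necitumumab for good (9.3.2.2.3.1.2 and Table JFCU.9.4). For thromboembolic events, 9.3.2.2.3.1.6 says that "the continuation of necitumumab therapy in these cases should be decided by the investigator after thorough risk-benefit assessment for the individual patient".

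**The concern.** Paragraph 2 ties its permission to events that are reversible and did not threaten life. Paragraphs 3 and 4 carry neither condition; their only filters are grade and possible relation to necitumumab. A site with a patient who has recovered from a related life-threatening event can find support in one section both for not re-treating and for resuming one level down.

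The stake is mainly patient safety. Protocol 5.2 reports that enrollment in the sponsor's nonsquamous Phase 3 trial was halted over thromboembolism and an imbalance in deaths, and about half of Part B is nonsquamous. Protocol 9.3.2.2.3.1.7 reports cardiorespiratory arrest or sudden death in 2.8% with necitumumab plus chemotherapy against 0.6% with chemotherapy alone.

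There is a smaller reporting consequence. SAP 5.7.3 lists adverse events leading to discontinuation and tabulates those leading to dose modification. The same kind of event could fall under either heading, depending on which paragraph a site followed.

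**Working it through.** No sample size, power or event count is involved, so the check sets the rules side by side.

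**Step 1: do the two sets of rules cover the same events?** The qualifier in paragraph 2 does some work only if some Grade 3 or higher events are life-threatening. Those events are excluded from paragraph 2. If possibly related to necitumumab, they are included in paragraph 3 or 4, which have no matching exclusion.

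**Step 2: do paragraphs 3 and 4 imply resumption?** They do not order it. But a suspension that runs until a stated recovery grade, followed by a one-level reduction, has no object unless dosing restarts.

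**Step 3: does a specific section settle each related life-threatening case?**

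| Event | Paragraph 2 | Paragraphs 3-4 | Event-specific text | Result |
|---|---|---|---|---|
| Grade 4 infusion reaction | outside | inside on its face | permanent stop | one instruction |
| Grade 4 skin reaction | outside | inside on its face | permanent stop | one instruction |
| Electrolyte abnormality, pneumonia or sepsis, cardiorespiratory event | outside | inside | sections exist, but none gives a necitumumab dosing rule | inconsistent |
| Any other toxicity | outside | inside | none | inconsistent |
| Thromboembolic event | outside | inside | investigator decides on continuation | precedence unclear |

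**Step 4: is there a general rule elsewhere that decides it?** Protocol 7.3.2 ends study treatment for unacceptable toxicity, but it does not name life-threatening events, and its example is a persistent moderate toxicity. Protocol 9.3.2.2.2 ends necitumumab after a delay of more than 6 weeks, which does not help for an event that recovers sooner. Neither settles the matter.

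**Step 5: the thromboembolic route.** The opening list in 9.3.2.2.3 omits these events. The introduction to 9.3.2.2.3.1 includes them, and 9.5.1 points there for serious ones. Paragraph 5 defers specific events to 9.3.2.2.3.1 for dose modifications, but 9.3.2.2.3.1.6 contains no dose. It covers whether to continue, not at what level.

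**Step 6: would the SAP detect divergence?** The predefined important violations in SAP 5.4 include necitumumab continued after a Grade 3-4 infusion reaction and more than two necitumumab reductions. They do not include re-treatment after other life-threatening events. Other deviations can be added only on review by the sponsor's clinical research physician.

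**The case against.** The strongest reply is that the paragraphs can be read together: paragraph 2 says when re-administration is open, and paragraphs 3 and 4 say what recovery and dose step then apply. Neither mandatory paragraph says that dosing must resume, and the investigator can always stop under 7.3.2. Part of this stands. The text does not expressly require re-treatment, and the word 'only' in paragraph 2 attaches to recovery, not to the kind of event. But the combined reading is not stated, and it fits poorly. Paragraph 2 sets its own recovery grade (2 or lower) and makes reduction optional; paragraph 4 sets a different one (baseline or at least Grade 1) and makes reduction compulsory. They do not read as two halves of one rule.

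Four stronger readings are tempting, and the documents do not support them.

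- *Every Grade 3 or higher event is caught.* The mandatory paragraphs cover only possibly related toxicity, and infusion and skin reactions have their own stop rules.
- *A thromboembolic event has three contradictory instructions.* Paragraph 5 defers specific events to 9.3.2.2.3.1. On an ordinary reading the specific section prevails on whether to continue, and investigator discretion is a single instruction. What remains is unclear precedence on the dose.
- *The protocol's thromboembolic rates size the problem.* The 9.5% (all Grade 3 or higher thromboembolic events) and 3.5% (Grade 3 or higher pulmonary embolism) in 5.2 come from first-line chemotherapy combinations and are not restricted to related or life-threatening events. The protocol also reports no thromboembolic signal with monotherapy or mFOLFOX6, and exclusion criterion [19] bars thromboembolism within the prior 3 months.
- *Site data become non-comparable.* The study is single-arm and hypothesis-generating, and the SAP plans no comparison between sites.

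**Conclusion.** The point holds in a limited form. Within 9.3.2.2.3, a related life-threatening toxicity that recovers is excluded from the permission to modify and re-administer, yet falls under a mandatory reduction that presupposes further dosing. This applies wherever no event-specific section gives a dosing rule. For thromboembolic events the defect is unstated precedence, not a further contradiction.

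Its size cannot be put as a patient count: the documents give no frequency of life-threatening necitumumab-related events outside the infusion and skin categories. No planned test or estimate depends on it. It deserves correction because two stated safety rules disagree, not because a detail is missing.

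The conclusion rests on two assumptions. The first is that life-threatening events are Grade 3 or higher. The wording of paragraph 2 presupposes that at least some are, although the protocol equates Grade 4 with life-threatening only in its hypersensitivity definitions. The second is that suspension until recovery followed by a reduction implies resumption. No view is taken on which rule is clinically right.

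**What to change.** Reconcile the text at the next amendment:

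1. In 9.3.2.2.3, state whether the limit to reversible, non-life-threatening events in paragraph 2 also governs the hematologic and nonhematologic paragraphs.
2. State whether 9.3.2.2.3 or 9.3.2.2.3.1.6 governs related Grade 3 or higher thromboembolic events, so that it is clear whether the one-level reduction applies when the investigator continues treatment.
3. Align the opening list of specific events in 9.3.2.2.3 with the list that introduces 9.3.2.2.3.1.
4. While the section is open, reconcile the recovery grade and the optional or mandatory status of the reduction between paragraph 2 and paragraphs 3-4.

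The sponsor's clinical team chooses the instruction; the need is that each such event has one. The cost is a wording change in two protocol sections, with no added patients or procedures.

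### For reversible, non-life-threatening, possibly related Grade 3 or higher necitumumab toxicity with no event-specific dosing rule, Protocol 9.3.2.2.3 gives inconsistent restart and reduction instructions and does not say which govern

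*Protocol*

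**What the plan says.** Protocol 9.3.2.2.2 sets a check before every dose: "Prior to each administration of necitumumab all toxicities associated with necitumumab must have resolved to Grade" 2 or lower, or to baseline, with alopecia and skin toxicity excepted. Two bullets follow, introduced by "If the criteria are not met at the time of a planned treatment". The first says that for necitumumab-related toxicity the drug is given at the reduced dose, with a pointer to 9.3.2.2.3, or is interrupted. The second sets a limit, "If administration of necitumumab is delayed for more than 6 weeks (2 cycles) after Day 1 of the most recent treatment cycle", with discontinuation of necitumumab as the consequence.

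Protocol 9.3.2.2.3 then gives general guidelines for toxicity associated with necitumumab:

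- Second paragraph, for non-life-threatening, reversible Grade 3 or higher events that need a delay of up to 6 weeks: "necitumumab may be readministered at a reduced dose (600 mg) if necessary only if AE is resolved to Grade" 2 or lower. It adds: "A second dose reduction (to 400 mg) is permitted for this level of event".
- Third paragraph, for possibly related Grade 3 or higher hematologic toxicity, a mandatory hold: "until the toxicity resolves to either baseline or at least Grade 2) and the dose of necitumumab must be reduced by 1 dose level".
- Fourth paragraph, for possibly related Grade 3 or higher nonhematologic toxicity, a mandatory hold with a stricter restart condition: "until the toxicity resolves to either baseline or at least Grade 1) and the dose of necitumumab must be reduced by 1 dose level".
- Later in the section: "Dose reductions (to 400 mg) are warranted in the setting of Grade 1-2 baseline symptoms or laboratory values", if these reach Grade 3 or higher on treatment.

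The third and fourth paragraphs point below for the dose levels, but no necitumumab list follows. The levels are in the second paragraph and in SAP Table JFCU.5.3 (800, 600, 400 mg). The section refers sites to 9.3.2.2.3.1 for named events. It does not rank its own general paragraphs.

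**The concern.** One event can fall under two paragraphs of the same section and receive different instructions. The second paragraph cannot be set aside as meant for unrelated events, because the section is introduced as guidance for necitumumab-associated toxicity.

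At stake are patient safety and necitumumab exposure. Two sites with similar patients could act differently after a severe event, and each could point to protocol text. The SAP would not bring this to light: the predefined important violations in SAP 5.4 include no item on restart grade.

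Such events are foreseeable. In the Phase 3 trial in nonsquamous disease described in Protocol 5.2, Grade 3 or higher asthenia occurred in 6.9% with necitumumab against 1.9% without it, vomiting in 6.6% against 3.2%, and diarrhea in 4.3% against 2.2%. None of the three has a necitumumab-specific dosing rule in 9.3.2.2.3.1. Those patients also received chemotherapy, so the figures show that such events happen; they do not predict rates here.

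**Working it through.** **The rules side by side**

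| Text | Restart condition | Dose at restart |
|---|---|---|
| 9.3.2.2.2, pre-dose check | Grade 2 or lower, or baseline | If the check fails: reduced dose, or interrupt |
| 9.3.2.2.3, second paragraph | Grade 2 or lower | 600 mg *if necessary* |
| Third paragraph (hematologic) | Baseline or at least Grade 2 | One level down, mandatory |
| Fourth paragraph (nonhematologic) | Baseline or at least Grade 1 | One level down, mandatory |
| Sentence on Grade 1-2 baseline findings | None given | 400 mg |

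**Where they disagree**

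- Nonhematologic, baseline Grade 0 or 1, event now at Grade 2: the second paragraph allows restart; the fourth requires the hold to continue.
- Nonhematologic, baseline Grade 2: every rule allows restart at Grade 2, so only the dose can differ.
- Hematologic: the restart grade agrees; only the optional or mandatory status of the reduction differs.

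**Size in one worked case**

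Assume Day 1 is given at 800 mg. A related nonhematologic event with no event-specific rule is Grade 3 at the Day 8 slot and Grade 2 from Day 10 through Day 13. Baseline is Grade 0, and the patient is reassessed within the window.

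- Planned dose per cycle: 2 × 800 = 1600 mg.
- Protocol 9.3.1 lets the Day 8 dose slip by up to 5 days: 8 + 5 = Day 13. After that it is omitted.
- A dose on Day 10 to 13 falls 9 to 12 days after Day 1 and 12 to 9 days before Day 22, so the 7-day minimum interval is met.
- Second paragraph, 600 mg: (800 + 600) / 1600 = 87.5%.
- Fourth paragraph, dose omitted: (800 + 0) / 1600 = 50%.
- Difference: 87.5 − 50 = 37.5 percentage points of that cycle's planned dose.

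An unreduced restart would give (800 + 800) / 1600 = 100%. It takes two readings together: that *if necessary* makes the reduction optional, and that the delay counts as an interruption under the first bullet of 9.3.2.2.2. Otherwise that bullet calls for the reduced dose.

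For a hematologic event with the same timing, the third paragraph gives 87.5%. The optional reading gives 100%, subject to the same two conditions: a difference of 12.5 points.

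**The 400 mg sentence**

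From 800 mg, one level down is 600 mg; 400 mg is two. With baseline Grade 2 and restart at Grade 2, the sentence gives (800 + 400) / 1600 = 75%, against 87.5% for one level. It is not labelled as an exception.

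**The case against.** The best defence is that the text can be read coherently. The check in 9.3.2.2.2 and the second paragraph of 9.3.2.2.3 are worded as necessary conditions. On that reading they set a general minimum, and the third and fourth paragraphs add class-specific requirements. A site that restarts at Grade 2 from a lower baseline would then breach an explicit requirement on the same page.

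Much of this stands. Following the third and fourth paragraphs satisfies all the restart-grade and reduction text except the 400 mg sentence, so a compliant course exists. But the protocol does not say that these paragraphs govern. If they do, *if necessary* has no role for related events, and Grade 2 has none for nonhematologic events with a lower baseline.

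The defence also limits the scope, rightly. Life-threatening events are outside the second paragraph. Skin and infusion reactions have their own rules, and continuation after a thromboembolic event is left to the investigator.

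A reader might infer that the protocol plainly authorises 800 mg at Grade 2. It does not: the only restart dose named in that sentence is 600 mg, and the first bullet of 9.3.2.2.2 points to the reduced dose.

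A reader might also infer that Grade 3 hypomagnesemia and conjunctivitis must follow the general hold-and-reduce rule because their own sections give no restart grade or dose. Those sections manage them by monitoring and repletion, and by ophthalmology referral. Whether a mandatory hold should be added is a medical decision that the text does not settle.

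**Conclusion.** The inconsistency is real and should be corrected. It is confined to reversible, non-life-threatening, possibly related Grade 3 or higher toxicity with no event-specific dosing rule. Within that group, the restart-grade conflict affects only nonhematologic events in patients whose baseline was below Grade 2. The conflict between optional and mandatory reduction affects both classes.

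The 37.5-point difference belongs to one cycle of one constructed case and depends on the timing assumed there. The documents give no rate for patients at Grade 2 at a dosing slot with a lower baseline, so no patient count can be given.

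Three stronger conclusions are not supported:

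- *Permanent discontinuation.* A reader might infer that a patient who stays at Grade 2 will be taken off necitumumab at 6 weeks. That limit follows from failing a check set at Grade 2 or lower, or baseline. The inference needs a site to apply it also to a hold under the fourth paragraph, which the protocol does not settle.
- *DLT status in Part A.* A reader might infer that 50% rather than 87.5% decides whether the 75% dose criterion in 9.3.2.1 is met. That criterion refers to both agents together and does not say how a shortfall in one counts.
- *The primary analysis.* The point has no effect on the 3-month PFS test or its sample size.

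**What to change.** In 9.3.2.2.3, delete *if necessary* from the second paragraph for related events, and add a precedence sentence along these lines:

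> For toxicity possibly related to necitumumab of Grade 3 or higher, the hematologic and nonhematologic paragraphs below determine the restart grade and require a reduction of one level (800 to 600 to 400 mg). The pre-dose check in 9.3.2.2.2 is a minimum and does not override them. Where 9.3.2.2.3.1 gives a dosing or continuation instruction for a specific event, that instruction takes precedence.

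Two tidying changes belong in the same amendment: label the 400 mg sentence as an exception or change it to one level, and replace the pointer to a missing list with the three dose levels. SAP Table JFCU.5.3 already has these levels and needs no change if the 400 mg sentence becomes one level. Leave the handling of hypomagnesemia and conjunctivitis to the sponsor's medical decision.

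In the worked case, the amended text gives one answer: 50% for the nonhematologic event and 87.5% for the hematologic one.

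The cost is a wording amendment and a communication to sites, with no new procedures. The clinical price is some longer holds and some omitted Day 8 doses for patients who would otherwise have restarted at Grade 2.
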